Individuals will be asked to return to the clinic at study weeks 1, 2, 4, and 6 after baseline to monitor for side effects and compliance. At the Week 4 visit, efficacy assessments will be completed (MADRS, YMRS and CGI-BP). Between clinic visits, research staff will complete phone calls with individuals at study Weeks 3, 5, and 7. Individuals will return for a final study visit 8 weeks after initiation of the randomized study medication. A Safety Follow-up phone call will take place 4 weeks after the final visit and safety assessments will be completed (C-SSRS, Adverse Events, Concomitant Medications). The assessments completed at baseline will be repeated at this Week 8 visit (See Appendix 1 – Schedule of Assessments). Reasons for early termination will be recorded. Every effort will be made to obtain appropriate rating scale data at the final visit of early terminators.

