#### 9.4.2 Cognition battery

The "Cleveland" cognition battery will be administered in this trial, which the PI has used over the past 30+ years as measures of the following cognitive domains: executive functioning, speed of processing, attention/vigilance, working memory, verbal learning, visual learning, reasoning and problem solving

This battery includes the following assessments:

- Wisconsin Card Sorting Test (WCST)
- Digit Symbol Task
- Rey Auditory Verbal Learning Test (Rey-AVLT)
- WISC-III Mazes
- Category Fluency Test
- Verbal Fluency

18

Brown-Peterson Consonant Trigram Memory Task

The cognition battery will be administered at baseline and end of study.

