## 11.0 Data and Specimen Management

#### 11.1 Data Analysis Plan

The primary analysis will be a mixed model repeated measures ANCOVA adjusting for baseline differences in dependent measures, sex and race. Missing data will be imputed by MMRM. We would also examine some variables categorically.

Assumptions for the power analysis included random assignment into one group receiving placebo and one JNJ-18038683. The cognitive battery, as the primary instrument, will be collected at baseline and at end point (8 weeks). Using repeated measure ANCOVA, the time average difference in the response variable will be compared between groups to detect treatment difference. Based on Javitt et al, 2012, we assume the mean baseline verbal learning score will be 36.2, SD 9.4 for both groups. We are assuming the placebo group will show no improvement while the treatment group will improve a mean of 5 points, a medium effect. We assume the correlation coefficient of repeated observation to be 0.5 and the covariance structure to be compound symmetry. The power calculation was conducted with alpha level of 0.05 using one-sided and two-sided tests. Full results are available upon request. With a one sided test, 33 individuals per group are required assuming 5 points improvement of the treatment group compared to the placebo for the desired power of 80% with alpha level of 0.05. We plan to recruit 36 per group to account for drop outs. In the two sided test the sample size per group is 42.

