Data Analysis Plan for Northwestern- Janssen R&D Collaboration Study

Protocol Title: Testing the ability of JNJ-18038683, a selective serotonin (5-HT)7 antagonist, to

improve cognition and reduce residual depressive symptoms in stable bipolar patients

Protocol Identifier Number: 18038683BCD2001

Northwestern University IRB Number: STU00200919-MOD0042

Version: 1.13

Date: 08.04.2021

Goals:

The goals of this study are to evaluate the efficacy of JNJ-18038683 in an 8-week trial to ameliorate the cognitive deficit and reduce residual depressive symptoms in 60 stable bipolar outpatients receiving treatment for depression. JNJ-18038683 will be studied and compared with placebo as adjunctive treatment to standard pharmacologic treatment for bipolar disorder. Sixty patients will be enrolled and randomized with a 1:1 ratio to one dose of JNJ-18038683 or placebo providing 30 subjects for each treatment arm. The initial intention was to follow stratified randomization based on the presence/absence of atypical APDs with 5-HT7 antagonism so that there is a balance in the assignment of active treatment and placebo in individuals who are and are not, receiving atypical APDs with 5-HT7 antagonism. However, due to recruitment difficulties, the stratified randomization method was not able to be followed as anticipated and was amended.

Assessments and Events:

Demographics, medical history, physical examination, serum pregnancy test, urine drug test, SCID-I diagnosis, and screening neurocognitive assessments will be done only during the screening visit. Urine pregnancy testing is performed at the baseline visit.

Table 1: Assessments completed during the screening visit only

Event /Assessment	Screen
Medical History & Demographics	X
Physical Examination	X
Serum Pregnancy Test	X
Urine Drug Screen	X
Inclusion/Exclusion Criteria	X
SCID-I	X
Screening neurocognitive assessments	X

Neurocognitive battery will be the primary measure of interest and evaluated at baseline and 8 weeks. The clinical global severity scores (CGI-BP), Young Mania Rating (YMRS), Scale for Tardive Dyskinesia (AIMS), Montgomery Asberg Depression Rating Scale (MADRS), Electrocardiogram and Clinical Safety Laboratory Tests will be collected at screening or baseline, and at 4 and 8 weeks. A measure of functional ability (SLOF) also will be assessed at baseline and 8 weeks. The schedule of these assessments is listed in table 2.

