The primary outcome measure for this study is verbal fluency performance as assessed with the Rey Auditory Verbal Learning Test, Rey Verbal Learning Test – Recognition Form, Verbal Fluency Test "Letterforms", and Animal Naming Test. The 8-week evaluation of verbal fluency after randomization is the primary outcome measure. Since the main interest is to measure the treatment effect for verbal fluency improvement from baseline and there is only one follow-up time point for the primary outcome variable, an ANCOVA model will be best suited for this study to compare the treatment effect using baseline value as a covariate. Alternatively, an ANOVA model will be used to compare the percent improvement and changes in the verbal fluency scores across treatment groups. Also, we plan to compare the treatment effect on verbal fluency performance over time using a mixed model. The missing evaluations will be imputed with the last value carried forward method, while model fit statistics will be used to estimate the appropriate covariance structure for this model.

There is both preclinical and clinical evidence that age has an important influence on 5-HT7 receptor function, which is the target of JNJ-18038683. Capacity to respond to JNJ-18038683 may decline with age. Thus, we predict the age of the subject will be related to the extent of improvement in verbal fluency and other measurements in the cognition battery. The relationship of age and percent improvement and the direct change of verbal fluency from baseline to 8 weeks in each treatment arm will be assessed using correlation analysis. The age variable will be used as a continuous variable in the analysis. If the distribution of the age variable is skewed, then age groups will be formed appropriately. In the above described ANCOVA and repeated measures models, age will be use as a covariate to assess the treatment effect. Graphical methods will be used to check for any inflection points of improvement of verbal fluency score in the treatment group compared to placebo. In the treatment group, better improvement is expected in younger patients compared to older patients. This relationship is not expected in placebo-treated patients. Additionally, with the above-mentioned models, the effect of covariates, MADRS total score, YMRS and Clinical Global Severity score on cognition will be examined because baseline mania or depression severity may influence performance on cognitive testing.

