Secondary analyses related to efficacy:

The secondary analyses regarding change in verbal fluency test scores will include identification of patients in each arm who improved in verbal fluency scores. The analysis plan includes exploring the effect of concomitant meds, gender or race that might contribute to treatment response. For this purpose, improvement in verbal fluency can be grouped as a dichotomous response and used as a dependent variable in a logistic regression model. The usual method of grouping will be improvement of ≥0.5 SD from the baseline scores. Using this model, the odds of improvement in verbal fluency can be compared in the active treatment group against the placebo group. In this model, the variables, age, gender, lab values and presence/absence of concomitant meds, baseline MADRS total score, YMRS and Clinical Global Severity score mania or depression severity may influence performance on cognitive testing and will be tested as potential covariates using one or few covariates at a time due to sample size restrictions.

Additional secondary analyses will study the effect of treatment group on other cognitive and behavioral measures including: 1) Digital Symbol Task, 2) Brown-Peterson Consonant Trigram Memory Task, 3) WISC-III Mazes; 4) Wisconsin Card Sorting Test; 5) MADRS total score,6) YMRS, and 7) Clinical Global Severity score using a mixed model repeated measure ANCOVA as described above. If indicated, variables such as age, gender, concomitant meds, will be examined, as will be done for the primary outcome measure.

Adverse Events:

A tabular summary of all anticipated and unanticipated serious or non-serious adverse events will be presented, including drop-outs due to any side effects or safety reasons. For each serious or other adverse events, the summary includes the adverse event term, affected organ system, number of participants at risk, and number of participants affected, by the study arm or comparison group. Using appropriate parametric or non-parametric methods, each type of adverse event will be compared between groups. All adverse events, e.g. development of suicidal ideation or behaviors or switch to mania/hypomania, will be examined thoroughly for impact on primary and secondary outcome measures. We will assess group differences, excluding subjects without these two side effects.

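### Last value carried forward scores an untested patient as zero cognitive change, conflicts with the protocol's mixed model, and has no stated scope

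*SAP*

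**What the plan says.** The SAP (Primary analysis for efficacy) takes as its main analysis an ANCOVA of the Week 8 score with baseline as covariate, because "there is only one follow-up time point for the primary outcome variable". It then offers an ANOVA of change and percent improvement, and adds a mixed model over time. The next sentence reads "The missing evaluations will be imputed with the last value carried forward method". That same sentence goes on to the covariance structure of a single model, which can only be the mixed model. Under Secondary analyses related to efficacy, four further cognition tests, with MADRS, YMRS and the global severity score, are analysed "using a mixed model repeated measure ANCOVA as described above".

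On timing, the SAP (Assessments and Events) states "Neurocognitive battery will be the primary measure of interest and evaluated at baseline and 8 weeks", and protocol Section 9.4.2 states "The cognition battery will be administered at baseline and end of study". Protocol Appendix 1 and SAP Table 2 agree. The schedule in protocol Section 7.0 also marks the battery at screening, which is still before treatment.

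Protocol Section 11.1 makes a mixed model repeated measures ANCOVA the primary analysis and says "Missing data will be imputed by MMRM". On drop-out it gives no rate, only "We plan to recruit 36 per group to account for drop outs", against 33 required. For early terminators, Section 9.0 says "Every effort will be made to obtain appropriate rating scale data at the final visit of early terminators"; it does not name the cognition battery.

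**The concern.** There are three linked problems.

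1. With one post-baseline test, the only value that can be carried to Week 8 is a pre-treatment score. A patient never retested is therefore analysed as if measured at Week 8 and found unchanged. If the rule also reaches the responder model in the secondary analyses, that patient falls below the 0.5 SD cut-off and counts as not improved.
2. The protocol and the SAP give different missing-data rules for the same endpoint, and neither says that it replaces the other.
3. The rule's scope is open. If it covers only the mixed model, the main ANCOVA has no missing-data rule. If it covers everything, the primary result includes invented zeros. Either way, the primary analysis cannot be reproduced from the text.

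At stake are the size of the estimated drug effect, its standard error and, if drop-out differs between arms while scores rise on retest, the type I error.

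**Working it through.** **Inputs from the documents.** Protocol Section 11.1: difference D = 5 points, no change on placebo, SD 9.4, correlation 0.5, alpha 0.05, 33 per group one-sided, 42 two-sided, 36 to be recruited. Protocol Section 22.0: 30 randomised per arm. The inputs describe a verbal learning score, and I use them as the plan does.

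**The plan's own figure.** For a time-averaged difference under compound symmetry the effective SD is 9.4 × √((1 + 0.5)/2) = 8.141. This gives 33 per group one-sided with power 0.80235, and 42 two-sided. Both match. The ANCOVA residual SD, 9.4 × √(1 − 0.5²), is also 8.141. None of this depends on the missing-data rule.

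**Implied drop-out.** 1 − 33/36 = 8.3%.

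**Target.** Neither document states an estimand. I assume the Week 8 effect had every patient been tested on treatment, with drop-out unrelated to scores.

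**Closed form.** Let dT and dP be the proportions untested on drug and placebo, and c a change common to both arms, such as a retest gain. With baseline carried forward, mean change is (1 − dT)(c + D) on drug and (1 − dP)c on placebo. The expected estimate is

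D − dT·D + (dP − dT)·c,

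so the bias is −dT·D + (dP − dT)·c.

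- 8.3% in both arms, c = 0: 5 × (1 − 0.0833) = 4.58.
- 20% in both arms: 5 × 0.80 = 4.00.
- 25% drug, 10% placebo, c = 3: 5 − 1.25 − 0.45 = 3.30.
- 10% drug, 25% placebo, c = 3: 5 − 0.50 + 0.45 = 4.95.
- D = 0, 10% drug, 25% placebo: 0.15 × 3 = 0.45 for c = 3; 0.15 × 5 = 0.75 for c = 5.

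**Simulation.** 20,000 trials per setting, 30 per arm, bivariate normal baseline and Week 8 scores, drop-out at random. Only the first row uses document inputs throughout. Drop-out rates in the other rows, and every non-zero c, are assumptions. Results are for ANCOVA on carried-forward data against ANCOVA on observed Week 8 scores.

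| D | Drop-out drug / placebo | c | Estimate, carried v observed | Two-sided power or error, carried v observed |
|---|---|---|---|---|
| 5 | 8.3% / 8.3% | 0 | 4.61 v 5.02 | 59% v 60% |
| 5 | 20% / 20% | 0 | 4.01 v 5.02 | 51% v 54% |
| 5 | 20% / 20% | 3 | 4.0 v 5.0 | 48% v 54% |
| 5 | 25% / 10% | 3 | 3.30 v 5.00 | 34% v 55% |
| 5 | 10% / 25% | 3 | 4.97 v 5.04 | 67% v 55% |
| 0 | 10% / 25% | 0 | 0.0 v about 0 | 5.2% v about 5% |
| 0 | 10% / 25% | 3 | +0.45 v about 0 | 5.7% v about 5% |
| 0 | 10% / 25% | 5 | +0.76 v 0.02 | 6.8% v about 5% |

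One-sided power in the first row is 71% v 72%. One-sided error in the last two rows is 8.1% and 10.5%, against about 5% for observed data. The 5.2% in the c = 0 row is within simulation error of 5% (standard error √(0.05 × 0.95/20,000) = 0.15 percentage points).

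**Standard errors.** Carried forward v observed: 2.1 v 2.2 at 8.3%, and 2.0 v 2.4 at 20%. The rule gives a narrower interval around a shifted value.

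**If the rule governs only the mixed model.** The baseline-to-Week 8 contrast on carried-forward data gives the same estimates: 4.61, 4.01, 3.30 and, for D = 0 with c = 5, 0.76.

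**The case against.** The strongest objection is that the SAP may not apply this rule to the primary test at all. The sentence follows the mixed model and closes by referring to one model, so the mixed model is the natural reading, and the ANCOVA then has a gap rather than a wrong rule. Carrying the rule into the secondary analyses is also an inference, since the back-reference may mean only the form of the model. MADRS, YMRS and the global severity score have a Day 28 value, so the zero-change argument does not hold for them in general.

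On size, the protocol's own inputs give a loss of 0.4 points and about one percentage point of power, with no inflation of type I error when c = 0. The larger figures need a retest gain and unequal drop-out that neither document states, and Section 11.1 assumes no placebo improvement. Even 8.3% may be too high as a rate of missing tests, because some early terminators may be tested at their final visit.

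Finally, the simulated drop-out is unrelated to scores, so observed-data ANCOVA is bound to look unbiased. With one post-baseline test and baseline as covariate, a patient without Week 8 data adds no outcome information to a mixed model either. The protocol's rule and the remedy are in effect analyses of those tested, with their own untestable assumption.

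Most of this stands as a limit on size and does not remove the point. On the narrow reading the shrinkage appears in the mixed model, and the primary ANCOVA has no rule. The conflict with the protocol holds on either reading. The completers' assumption is real, and it calls for a sensitivity analysis rather than a rule that fixes every untested patient at zero change.

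**Conclusion.** The concern holds and should be fixed. It is certain that carrying forward gives zero change to anyone without a post-baseline battery, that the SAP and protocol Section 11.1 disagree, and that the scope is not stated.

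The effect on the result is less certain. Under the target assumed above and the protocol's inputs it is a modest shrinkage towards zero, 4.6 against 5.0 points. It grows in proportion to drop-out on drug. It can favour the drug only if there is a common gain on retest and more placebo than drug patients go untested. If patients who stop treatment lose benefit, the target itself differs, and zero change becomes an untested assumption about them.

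**What to change.** - State the missing-data rule for each model by name: the ANCOVA, the ANOVA of change and percent improvement, the mixed model, the 0.5 SD responder model, and the secondary cognition models.
- Remove carrying forward from the ANCOVA and mixed models for cognition. Analyse observed Week 8 scores by ANCOVA with baseline as covariate, or by a likelihood mixed model without imputation, and state the missing-at-random assumption.
- Say whether the battery is given at early termination and, if so, whether that score counts as the Week 8 outcome.
- Align protocol Section 11.1 with the SAP. The protocol wording also needs correcting, because a likelihood mixed model does not impute.
- Keep carrying forward, if at all, as a labelled sensitivity analysis beside one other, for example imputation with a range of worse outcomes for untested patients.

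The cost is SAP wording and a few lines of code, with no new data. The standard error will be wider (2.2 v 2.1 at 8.3% drop-out, 2.4 v 2.0 at 20%). In some patterns nominal power will be lower than carrying forward would show: 55% v 67% with 10% drop-out on drug, 25% on placebo and a 3-point common gain.

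### The SAP predicts that age modifies the drug effect on verbal scores, but none of its planned age analyses estimates or tests the difference in age slopes between the arms

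*SAP*

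**What the plan says.** The prediction is in the SAP under Primary analysis for efficacy, in the paragraph on age: "In the treatment group, better improvement is expected in younger patients compared to older patients. This relationship is not expected in placebo-treated patients". The SAP supports it with a mechanism, namely that age influences the receptor the drug targets.

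The planned age analyses are:

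- **Correlation, one arm at a time:** "The relationship of age and percent improvement and the direct change of verbal fluency from baseline to 8 weeks in each treatment arm".
- **Age in the ANCOVA and repeated-measures models:** "age will be use as a covariate to assess the treatment effect". No product term with treatment is named.
- **Plots:** "Graphical methods will be used to check for any inflection points of improvement of verbal fluency score in the treatment group compared to placebo".
- **Coding of age:** continuous by default, with a fallback: "If the distribution of the age variable is skewed, then age groups will be formed appropriately". No cutpoints are given.
- **Secondary responder model:** under Secondary analyses related to efficacy, age is one of several variables that "will be tested as potential covariates using one or few covariates at a time due to sample size restrictions".

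Protocol section 11.1 does not mention age. Its model is described as "adjusting for baseline differences in dependent measures, sex and race". The outcome is a set of four verbal measures rather than one: "The primary outcome measure for this study is verbal fluency performance as assessed with the Rey Auditory Verbal Learning Test", followed by three further tests.

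**The concern.** A slope on drug and no slope on placebo is a statement about a difference between slopes. Two within-arm correlations give two separate answers and no contrast. A common age covariate fits one slope to both arms, so the predicted difference is not in the model. The plots compare the arms by eye, without an estimate or an interval.

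The within-arm results can count against the prediction, through a flat slope on drug or a clear slope on placebo. They cannot show that age modifies the drug effect, because a difference in significance between arms does not show that the slopes differ. At stake is whether a stated hypothesis, placed under the primary efficacy heading, gets an answer with its uncertainty attached.

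**Working it through.** **1. The plan's own figures.** The documents give no figure for any age analysis. The sample size in Protocol 11.1 concerns the main effect: SD 9.4, correlation 0.5, two time points, difference 5.

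- SD of the time average = 9.4 × √((1 + 0.5)/2) = 8.14.
- One-sided: n = 2 × (1.645 + 0.842)² × 8.14² / 5² ≈ 32.8, so 33 per group. The exact power at 33 is 0.802.
- Two-sided: n = 2 × (1.960 + 0.842)² × 8.14² / 5² ≈ 41.6, so 42 per group.

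Both reproduce. They say nothing about age.

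**2. What each planned analysis delivers.**

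| Planned analysis | Gives | Difference in slopes? |
|---|---|---|
| Correlation within arm | one r per arm | no contrast |
| Age as covariate | one common slope | not in the model |
| Plots for inflection points | visual comparison | no estimate or interval |
| Age in the logistic model | one common log-odds slope | not in the model |

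**3. If the two correlations were read by significance.** This decision rule is an assumption. Take 30 per arm (SAP, Goals) and two-sided 0.05. A correlation is significant beyond |r| = 0.361, which is 0.378 on the Fisher z scale, with standard error 1/√27 = 0.192.

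Example with r = -0.3 in both arms: atanh(0.3) = 0.310. P(significant negative) = Φ((-0.378 + 0.310)/0.192) ≈ 0.361. P(significant on drug, not on placebo) = 0.361 × (1 - 0.361) ≈ 0.231.

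Simulation (100,000 trials per setting), with the same true correlation in both arms:

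| Common r | Significant negative on drug, not significant on placebo |
|---|---|
| 0 | 2.4% |
| -0.1 | 7% |
| -0.2 | 15% |
| -0.3 | 23% |
| -0.4 | 24% |
| -0.5 | 14% |
| -0.6 | 4% |

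The peak is about 25%, near r = -0.36. A direct between-arm comparison in the predicted direction rejects in about 2.5% throughout.

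**4. What a direct estimate would give.** Inputs: SD 9.4 and correlation 0.5 (Protocol 11.1, verbal learning; the SAP gives none for its four scores), and ages uniform over 18 to 60. The age limits are those of Protocol 3.1; the uniform shape is an assumption. The model is the Week 8 ANCOVA with treatment, baseline, age and treatment-by-age.

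- Residual SD = 9.4 × √(1 - 0.5²) = 8.14.
- Age SD = 42/√12 = 12.1, so the variance is 147.
- At 30 per arm: SE of the slope difference = 8.14 × √(2/(29 × 147)) = 0.176 per year, or 1.76 points per 10 years. With 55 df, t = 2.004, so the 95% CI half-width is 3.5 points per 10 years.
- At 25 per arm (assumed completers): SE = 8.14 × √(2/(24 × 147)) = 0.194 per year. With 45 df, t = 2.014, so the half-width is 3.9.
- 80% power at 30 per arm needs about (2.004 + 0.85) × 1.76 ≈ 5.0 points per 10 years. Over the 42-year age range that is 5.0 × 4.2 = 21 points, against an assumed mean drug effect of 5.

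On the correlation scale, without baseline adjustment, a slope on drug only is detected with power of about 20%, 33% to 34%, and 50% for r of -0.3, -0.4 and -0.5.

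**The case against.** **The SAP states no rule for reading the correlations.** This stands. It sets no significance criterion and does not say that one significant and one non-significant correlation would establish moderation. A reader might infer that the plan carries a false-positive rate of up to about a quarter. The documents do not support that, because the rates in step 3 describe a possible misreading and not a planned test.

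**The excess also needs an age slope on placebo.** This stands too. The SAP expects none, and Protocol 11.1 assumes no improvement on placebo. Age-dependent practice effects are a possible source, but neither document raises them.

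**The information is not lost.** This stands in part. With r and n from both arms a reader could compute a Fisher z contrast, and the plots do set drug beside placebo. But the plan commits to no such contrast, and a difference in unadjusted correlations is not the baseline-adjusted difference in slopes. The word covariate could be stretched to include an interaction, but the text does not say so.

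**The remedy has little power.** True. That is a reason to show the interval, since two p-values at 30 per arm hide the imprecision.

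**Age groups can help show a threshold.** This stands for display. The fallback is conditional on skewness and no particular split is named, so no definite power loss can be charged to the SAP.

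**Conclusion.** The concern holds in a limited form. The SAP predicts a difference in age slopes between the arms and, followed exactly, never estimates or tests it. This rests on the text alone and needs no assumed figure.

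The numerical consequence is conditional on three assumptions: an unstated reading rule, an equal non-zero age correlation in both arms, and 30 per arm. If the SAP is right that placebo has no age slope, and the drug has none either, there is no excess of false positives. The loss is then the estimate and its interval.

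A reader might also infer that the main treatment comparison is compromised. It is not: adjusting a randomized comparison for age with a common slope leaves it valid. This is a cheap improvement of low to moderate severity.

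**What to change.** Add to the age paragraph of the SAP:

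> For each verbal score analysed as primary, an exploratory model will add age (continuous, mean-centred) and a treatment-by-age term to the Week 8 baseline-adjusted ANCOVA. The slope difference between arms will be reported with its 95% CI for every such score, and the number of scores examined will be stated. Any statement that age modifies the drug effect will rest on these estimates. Within-arm correlations and plots are descriptive.

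Keep the main treatment comparison in the model without the interaction. Use continuous age in the exploratory model even if age is skewed, since regression does not need a symmetric covariate; age groups may still be shown descriptively. Holm adjustment across scores is optional for an exploratory analysis.

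The cost is one extra model per score and a few sentences, with no new data. The downside is a wide interval and low power (step 4), so a null result would be inconclusive. A linear term can also miss a threshold pattern, which is why the plots should stay. The text should be fixed before unblinding; if added later, the analysis should be labelled post hoc.

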#### 3.1 Inclusion Criteria

- All participants must have signed an informed consent document indicating they understand the purpose of the study and the procedures required for the study and are willing to participate by complying with the study procedures and restrictions.
- 2. Male or female individuals of any race; between 18 to 60 years of age, inclusive.
- 3. Resides in a stable living situation, according to the investigator's judgment.
- 4. Diagnosis of bipolar disorder I or II for at least 1 year in duration, as established by the SCID-I, and verified with medical records and/or confirmation of diagnosis by treating clinician. Patients will be in a nonacute phase at the time of initial screening and have been so for at least 1 month.
- 5. No more than moderate clinical symptom burden severity, as defined by the following:
  - Montgomery Asberg Depression Rating Scale ≤ 20
  - Young Mania Rating Scale ≤12
- 6. Individuals medically stable enough to complete an 8 week clinical trial, in the judgment of the investigator

- 7. Women of childbearing potential must have a negative pregnancy serum test at screening, negative pregnancy urine test at baseline, and agree to use adequate protection (i.e. double barrier method) for birth control.
- 8. Antidepressant (AD) medications are allowed if the subject has been treated with a stable dose for at least 2 months before screening.
- 9. Individuals receiving a single mood stabilizer (e.g., lithium. valproate, or lamictal) are allowed if a stable dose has been maintained for at least 2 months prior to screening.
- 10. Individuals may be receiving one treatment of each the following groups: antidepressants, mood stabilizers, and atypical antipsychotics other than clozapine, but not more than one from each group.
- 11. Individuals taking ripseridone, lurasidone, or ziprasidone must be currently taking solder: doses of 3mg, 40mg, and, 80mg, respectively.
- 12. Subjects may be treated with inclusionary antipsychotic drugs as long as they are on a stable dose of injectable medication for 2 months or a sable dose of an oral medication for 1 month. Exclusionary antipsychotic drugs are listed in Appendix 2.
- 13. Patients with a history of compliance with a drug treatment regimen for bipolar disorder, as noted in medical/psychiatric history.

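### Skewness is not a reason to replace continuous age with unspecified age groups: the rule costs power in the age-response analysis and leaves the cut-points open

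*SAP*

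**What the plan says.** The age paragraph under Primary analysis for efficacy in the SAP predicts that response to the drug declines with age: "In the treatment group, better improvement is expected in younger patients compared to older patients". No such relation is expected on placebo. The relation of age to percent improvement and to change from baseline "in each treatment arm will be assessed using correlation analysis". Age also enters the ANCOVA and repeated measures models, where "age will be use as a covariate to assess the treatment effect".

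The default is clear: "The age variable will be used as a continuous variable in the analysis". The next sentence sets the exception: "If the distribution of the age variable is skewed, then age groups will be formed appropriately". The SAP gives no measure or threshold of skewness, no number of groups, no cut-points, and no time by which they must be set. Later in the same paragraph it adds: "Graphical methods will be used to check for any inflection points of improvement of verbal fluency score in the treatment group compared to placebo". The protocol's Data Analysis Plan (section 11.1) adjusts for baseline, sex and race and does not mention age, so it does not fill the gap.

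**The concern.** The rule answers a problem that does not exist. The models condition on age, and their assumptions concern the residuals and the form of the relation, not the shape of the age distribution. A few extreme ages could carry much weight in a Pearson correlation, but ranks deal with that without forming groups.

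The rule brings two risks of its own. Grouping discards the variation in age within groups, so a real gradient is easier to miss. Open cut-points, in a paragraph that also looks at outcome plots by arm, leave room for an apparent age threshold to be picked from the data. Age is the one patient characteristic for which this paragraph predicts a different response, with a stated direction. A reader of the results could not tell a pre-set age grouping from a selected one.

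**Working it through.** **Inputs.** From the documents: eligible ages "between 18 to 60 years of age, inclusive" (Protocol 3.1); randomisation "providing 30 subjects for each treatment arm" (SAP, Goals). Neither document gives a figure for the age analysis, so there is none to reproduce. Assumed: the shape of the age distribution (beta shapes scaled to 18–60 and a truncated exponential), a linear relation with true correlation 0.4, and a two-sided 0.05 test.

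**Step 1. Information kept by grouping.** The share of linear age information kept is the squared correlation between age and its group mean:

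k = Var(group mean of age) / Var(age).

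A check by hand with uniform ages: the two halves have means 28.5 and 49.5, so the between-group variance is 0.25 × 21² = 110.25. The total variance is 42²/12 = 147, so k = 110.25/147 = 0.75.

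For skewed ages on 18–60:

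| Assumed shape | Skewness | k, median split | k, tertiles | k, quartiles |
|---|---|---|---|---|
| Beta(2, 4) | 0.47 | 0.667 | 0.825 | 0.889 |
| Beta(1.2, 3) | 0.70 | 0.658 | 0.820 | 0.886 |
| Truncated exponential | 1.14 | 0.585 | 0.764 | 0.846 |
| Beta(1, 5) | 1.18 | 0.586 | 0.757 | 0.834 |

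The loss is 1 − k: 33–42% for a median split, about 18–24% for tertiles and 11–17% for quartiles.

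**Step 2. Power of the within-arm test, n = 30.** Grouping shrinks the correlation from r to r√k. With the Fisher transformation,

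power ≈ Φ(√(n − 3) × atanh(r√k) − 1.96), with √27 = 5.196.

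- Continuous age, k = 1: 5.196 × atanh(0.400) = 5.196 × 0.4236 = 2.20, so power ≈ Φ(0.24) = 0.60.
- Median split, k = 0.667: 5.196 × atanh(0.327) = 5.196 × 0.3391 = 1.76, so power ≈ Φ(−0.20) = 0.42.
- Tertiles, k = 0.825: 5.196 × atanh(0.363) = 5.196 × 0.3807 = 1.98, so power ≈ Φ(0.02) = 0.51.

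Simulation with the two moderate skews (20,000 trials) agrees: 60–61% continuous, 54–55% Spearman, 50–51% tertiles and 42% median split. A separate run put the median split at about 41%.

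**Step 3. False positives if cuts follow the outcome.** With no age effect and n = 30, one pre-set cut keeps the error at 5%. Reporting the best of several cuts gives:

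- best of 3: 11–12%
- best of 5: 15–16%
- best of 13 between the 20th and 80th percentiles: about 24%
- any cut leaving at least 5 patients on each side: 29%

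As a plausibility check, three independent tests would give 1 − 0.95³ = 14%. Overlapping groups bring this down to about 11%.

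**Step 4. The age-adjusted treatment comparison.** If age has correlation r with the residual outcome and grouping keeps a share k, the standard error of the treatment effect is multiplied by √[(1 − k r²)/(1 − r²)].

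- r = 0.3, k = 0.55: √(0.9505/0.91) = 1.022
- r = 0.3, k = 0.80: √(0.928/0.91) = 1.010
- r = 0.4, k = 0.55: √(0.912/0.84) = 1.042
- r = 0.4, k = 0.80: √(0.872/0.84) = 1.019

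The increase is 1–4%.

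**The case against.** Continuous age is the default, and grouping is only a fallback. The SAP speaks of groups, not of two groups. Age is a baseline variable, so groups can be formed blind to outcome and arm. The age relation supports the efficacy analysis and is not the treatment comparison; with no treatment-by-age interaction stated, how age is coded might seem a second-order matter.

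Much of this stands, and it rules out three stronger readings that a reader might infer:

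- *That grouping throws away about half the age information, so that 60 patients count as about 30.* A median split loses that much only under a skew close to an untruncated exponential (skewness 2, k = 0.48), which ages limited to 18–60 do not easily allow. An off-median split in two can also lose about half: a cut at age 40 under moderate right skew loses 47–48%. The SAP specifies neither.
- *That the SAP plans to choose cut-points from the outcome plots.* It does not link the plots to the forming of groups. Its wording leaves this open and no more.
- *That the primary treatment comparison is compromised.* Step 4 shows a small loss of precision, and randomisation keeps the comparison unbiased.

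The objection does not rescue the rule itself. The fallback is triggered by a feature that needs no remedy, and even well-chosen groups formed blind lose power against continuous age. The missing interaction term is a separate question; grouping would weaken that analysis too.

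**Conclusion.** The point holds for the age-response analysis. When the rule is triggered, it costs about a third to two fifths of the linear age information with a median split and about 10–25% with three or four groups. At an assumed correlation of 0.4 with 30 per arm, a median split takes power from about 61% to about 41–42%, where Spearman would keep about 54%. Because cut-points and their timing are open, the false-positive rate for an age threshold could reach about 11–24% (best of 3 to 13 cuts). That is a worst case that the wording permits, not what the plan produces.

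These sizes rest on assumed age shapes, a linear relation and a full 30 patients per arm; dropout would lower all the power figures. That skewness is no reason to group, and that the cut-points are unspecified, depends on none of these assumptions.

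**What to change.** Delete the sentence on forming age groups. State instead that:

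- age stays continuous in every model, whatever its distribution;
- Spearman correlation is used in the within-arm analyses if age or change is skewed;
- any age groups serve for display only, with cut-points fixed and dated before unblinding.

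This changes a few lines of the SAP and needs no new data and no more patients. The one statistical cost is that Spearman has somewhat less power than Pearson when the relation is linear (about 54% against 61% in the case above), still well above a median split.
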